2 SUBJECT SELECTION AND WITHDRAWAL

This study plans to enroll 80 evaluable subjects (40 evaluable patients in each cohort) over 7 years. For pre-operative patients, evaluability requires a minimum of 4 months of follow-up after surgery. For post-operative patients, evaluability requires a minimum of 2 years of follow-up from the end of radiotherapy.

Inclusion Criteria

- Patients with a histologic diagnosis of soft tissue sarcoma of the extremities are eligible for this study.
- Patient must be ≥ 18 years of age.
- Patients must have evidence of disease limited to the extremities.
- For the pre-operative group, patients must be considered operable/resectable and a candidate for pre-operative radiotherapy as judged by the attending surgeon and radiation oncologist. The clinical evaluation of patients will include a work up as per the standard of care. All patients in the pre-operative group will be evaluated for this protocol PRIOR to the initiation of therapy.
- For the post-operative group, patients must be considered operable/resectable (if evaluated prior to resection) and a candidate for post-operative radiotherapy by the attending surgeon and radiation oncologist. The clinical evaluation of patients will include a work up as per the standard of care. Patients in the post-operative group may be evaluated PRIOR to the initiation of any therapy or may be referred for evaluation after surgical resection.
- ECOG status of 0-2.
- Patients must sign a document that indicates that they are aware of the investigative nature of the treatment of this protocol, and the potential benefits and risks. Patients unwilling or unable to sign informed consent are excluded from the study.
- Women of child-bearing potential as long as she agrees to use a recognized method of birth control (e.g. oral contraceptive, IUD, condoms or other barrier methods etc.). Hysterectomy or menopause must be clinically documented.
- Negative urine pregnancy test for females of childbearing potential on the day of the F18-EF5 PET scan prior to F18-EF5 injection

Exclusion Criteria

- Pregnant women, women planning to become pregnant and women that are nursing.
- Patients who experience surgical complications that prevent radiation from starting for 5 months or more, unless there is evidence of gross residual disease.

Subject Recruitment and Screening

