4 SURGERY , CHEMOTHERAPY AND IMAGING

Radiation therapy will be performed either preoperatively or postoperatively. This decision will be made by the attending surgeon and radiation oncologist. For patients in the preoperative cohort, surgery will be performed 4-12 weeks after completion of radiotherapy. This will consist of resection of all gross tumor with adequate margins, sampling of lymph nodes and any other areas suspicious for involvement by the sarcoma as clinically appropriate. For patients in the postoperative cohort, radiotherapy will begin 3-8 weeks following surgery.

Chemotherapy (standard of care as determined by medical oncology) may be given no sooner than day 30 after radiation therapy for the post-operative patients or day 30 after surgery if radiotherapy is pre-operative as deemed clinically appropriate by the attending surgeon and radiation oncologist.

CONFIDENTIAL

18F-EF5 PET Scan

Up to 4 weeks prior to treatment with either surgery or proton radiation, ^{18}F -EF5 will be administered in the Department of Nuclear Medicine in the Hospital of the University of Pennsylvania (HUP) or in the Department of Radiation Oncology in the Perelman Center for Advanced Medicine. Approximately 5mCi of ^{18}F -EF5 will be administered as an IV bolus (for details of ^{18}F -EF5 synthesis, see specific methods, below). After the injection of ^{18}F -EF5, subjects will be asked to remain in the Nuclear Medicine or Radiation Oncology waiting room during the free time before their PET/CT scan, where they may relax until they are required to go to the PET/CT scan room. There is no bathroom restriction during this time. The Scan will be performed at 180 minutes (evaluation of hypoxia) following injection. Subjects will be positioned on the PET-CT imaging bed comfortably with their head secured in the head hold of the PET instrument.

TIME (APPROXIMATELY)	SCHEDULE OF EVENTS
-30 minutes	Transport to nuclear medicine facility
-10 minutes	Placement of one intravenous line
0 minutes	Injection of ^{18}F -EF5 (\approx 5 mCi)
1-179 minutes	Free time
180 minutes	PET/CT Scan
215 minutes	Study completed

Table 3: ^{18}F -EF5 PET Protocol**Expected Adverse Events Associated with radioactive ^{18}F -EF5.**

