- **Partial Response (PR):** At least a 30% decrease in the sum of the longest diameters of target lesion, taking as reference the baseline sum of the longest diameters.

CONFIDENTIAL

- **Progressive Disease (PD):** At least a 20% increase in the LD of the target lesions, taking as reference the smallest sum of the LD recorded since the treatment started or the appearance any new lesion(s)
- **Stable Disease (SD):** Neither sufficient shrinkage to qualify for PR nor sufficient increase to qualify for PD, taking as reference the smallest sum LD since the treatment started.

Non-Target Lesions:

- **Complete Response (CR):** Disappearance of all non-target lesions and normalization of tumor marker levels.
- **Incomplete Response/Stable Disease (SD):** Persistence of one or more non-target lesion(s) and/or maintenance of tumor marker levels above normal limits.
- **Progressive Disease (PD):** Unequivocal progression of existing non-target lesions or any new lesion(s)

Confirmation of Response (used only for studies with response as primary endpoint)

- To assign a PR or CR, changes in tumor measurement must be confirmed by repeat assessments no less than 4 weeks after the criteria for response are first met. (*Reflect this in your study procedures table in section 6*)
- To assign SD, measurements must have met the stable disease criteria at least once after study entry at "X" interval (*as defined by protocol*).

Failure

- **Local failure** is defined as: evidence of tumor growth in any direction beyond that present of the pre-treatment imaging studies or the appearance of tumor in tissues previously scored as sites of subclinical disease. The imaging studies are to be comparable in technical factors.
- **Marginal failure** is defined as appearance of tumor growth at the margin of the target volume
- **Nodal Failure:** Failure in regional lymph nodes.
- **Distant failure** is defined as appearance of tumor at sites beyond regional nodal and marginal site.
- **Progression-Free Survival:** duration measured from first day of treatment to first documented failure, death due to any cause or last patient contact alive.
- **Overall Survival:** Duration measured from first day of treatment until death due to any cause or last patient contact alive.
- Time to local failure, time to distant failure, PFS and OS will be calculated from **first day of radiation** in the pre-operative patients and calculated from **day of surgery** in the post-operative patients.

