Publishers, 1964). Patients will be assessed for fibrosis, joint stiffness and edema within 2 years of completion of radiotherapy.

Clinical Efficacy is defined for pre-operative patients as overall response rate (CR + PR according to RECIST criteria) which is scored after radiation and before surgery. Progression-Free Survival is defined from first day of treatment to first documented failure, death due to any cause or last patient contact alive. Overall Survival is defined from first day of treatment until death due to any cause or last patient contact alive. Time to local failure, time to distant failure, PFS and OS will be calculated from first day of radiation in the pre-operative patients and calculated from day of surgery in the post-operative patients.

Rules for Early Termination for Feasibility, Acute Toxicity and Wound Complication:

Bayesian probability calculations will be employed to define rules of early termination and end of trial evaluation for feasibility and safety. The tables below indicate termination rules after groups of 3 patients have been treated. Hundreds of patients with certain types of cancer have undergone radiation therapy with protons. Thus, we will assume some "prior" feasibility and safety data for protons delivered at the standard radiation dose for our Bayesian calculations. We will assume prior information equivalent to that of 6 treated patients, which is commonly required to establish feasibility and safety in a standard 3+3 phase I trial design.

Feasibility – conducted separately for each stratum

We will assume a beta (5,1) prior, which is information equivalent to feasibility established in 5 of 6 treated patients. A feasibility rate > 90% is considered acceptable. If the number of patients deemed feasible is less than or equal to the number in the table below then termination will be considered as it is highly unlikely that the feasibility rate is > 90%, as noted by the Bayesian posterior probabilities.

Bayesian Rule for Feasibility				
Patients treated	3	6	9	12
Patients who are feasible	1	4	6	9
Posterior Prob[feasibility rate >90%]	0.0	0.0	0.0	0.0
Action	Terminate enrollment			

Acute Toxicity – conducted separately for each stratum * excludes wound complication *

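### Post-operative PFS, OS and distant-failure curves start at surgery without delayed entry, so patients enrolled after resection bias them slightly upward

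*Combined protocol and SAP*

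**What the plan says.** Section 6.1 (Clinical Efficacy) gives a general definition: "Progression-Free Survival is defined from first day of treatment to first documented failure, death due to any cause or last patient contact alive". OS is framed the same way. The next sentence sets the origin by cohort: first day of radiation for pre-operative patients, and for the others "calculated from day of surgery in the post-operative patients". It covers time to local failure, time to distant failure, PFS and OS. The failure definitions in Section 5 repeat both statements.

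Sections 6.1 and 6.3 estimate these times by Kaplan-Meier, separately by stratum. Section 6.3 also uses them in exploratory Cox models for hypoxia. Neither section mentions delayed entry, left truncation or a landmark.

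On entry, Section 2 says that post-operative patients "may be evaluated PRIOR to the initiation of any therapy or may be referred for evaluation after surgical resection". It also requires: "Patients must have evidence of disease limited to the extremities". Section 4 plans that "radiotherapy will begin 3-8 weeks following surgery". Section 2 excludes surgical complications that "prevent radiation from starting for 5 months or more", unless there is gross residual disease.

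**The concern.** A patient first referred after resection enters only if alive, without known spread beyond the extremity and still a candidate for radiotherapy. Patients who failed those conditions between surgery and referral never appear in the data. With the clock at surgery and no delayed entry, each late enrollee is nevertheless counted as at risk from day zero. The denominator is inflated over a period in which that patient could not contribute a death or a known distant failure.

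The error always runs in the treatment's favour and does not shrink as the sample grows, and the confidence interval does not reveal it. What is at stake is the descriptive account of PFS, OS and distant control after post-operative protons, which readers may set beside other series.

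**Working it through.** The plan states no rate, event count or power for these endpoints, so it has no figure of its own to reproduce. The check sizes the bias.

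**Inputs from the documents**
- Gap d from surgery to radiotherapy: 3-8 weeks (Section 4), which is 0.69-1.84 months. The outer value is 5 months, from the Section 2 exclusion.
- Evaluable post-operative patients: 40 (Section 6.4).

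**Assumptions, not in the documents**
- True 24-month event-free rate S24: 50% to 80%, with 90% added for a low-event endpoint.
- Constant hazard.
- Share f enrolled after resection: 100% as the extreme, 50% for comparison.
- Late enrollees enter just before radiotherapy, and any event before entry bars entry.

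**Formulas**
- h = -ln(S24)/24 per month, and S(d) = exp(-h d).
- For late enrollees, Kaplan-Meier from surgery without delayed entry estimates S24/S(d).
- Bias = f × S24 × (1/S(d) - 1).

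**Worked case.** Take S24 = 0.50, d = 1.84 months and f = 1. Then h = 0.6931/24 = 0.02888, S(d) = exp(-0.0531) = 0.948, and 0.50/0.948 = 0.527. The bias is 2.7 points.

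**Overstatement of the 24-month rate, in points, with all enrolled late**

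| True S24 | 3 weeks | 8 weeks | 5 months |
|---|---|---|---|
| 50% | 1.0 | 2.7 | 7.8 |
| 60% | 0.9 | 2.4 | 6.7 |
| 70% | 0.7 | 1.9 | 5.4 |
| 80% | 0.5 | 1.4 | 3.8 |
| 90% | 0.3 | 0.7 | 2.0 |

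With f = 0.5 every entry halves.

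**Simulation check** (40 patients, 4,000 runs, all enrolled late, gaps uniform over 3-8 weeks, clock from surgery). The mean 24-month estimates were 61.5%, 71.3% and 80.8% for true rates of 60%, 70% and 80%, an excess of 1.5, 1.3 and 0.8 points. The SD of the estimate was 7.8, 7.2 and 6.2 points. The bias is thus between 0.8/6.2 = 0.13 and 1.5/7.8 = 0.19 of one SD.

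**What each remedy does in the same simulation** (true rate 60%)
- Clock from first radiation: 59.9%. This matches the rate from surgery only because the assumed hazard is constant.
- Clock from surgery with delayed entry: 60.8% for gaps of 3-8 weeks, and 62.5% for gaps of 8 weeks to 5 months. Here nobody was at risk before the shortest gap, so the curve is conditional on being event-free to that point: 0.60/S(3 weeks) = 60.9% and 0.60/S(8 weeks) = 62.4%. Delayed entry recovers the full curve from surgery only if some patients are enrolled by the day of surgery, which Section 2 permits.

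**The case against.** The strongest reply is that surgery is a common and reasonable origin, the planned gap is short and nothing is decided on these curves. Most of that stands. PFS, OS and failure times are secondary (Section 1) and have no null rate, comparator or test. At 3-8 weeks the bias is well inside sampling error. It vanishes for patients enrolled before resection, whose share is not given. The reply does not remove the bias for late enrollees, because nothing in the plan corrects it.

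Four stronger readings are tempting, and the documents do not support them.

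- **A reader might infer that late entrants are guaranteed progression-free.** Section 3 allows gross residual disease in the post-operative target, and Section 2 waives the 5-month limit when it is present. The guarantee is strict for death and known distant spread, but weak for local failure. For PFS, the tabulated figures are therefore upper values in this respect.
- **A reader might infer that the hypoxia Cox models are generally biased.** Section 6.3 needs signal from the primary tumour, Section 4 places the scan before surgery or protons, and Section 12 requires consent before any study procedure. Post-operative patients with usable scans will mostly have enrolled before resection, when surgery is a valid origin. Only the few late enrollees with scannable residual tumour are affected.
- **A reader might object that the two cohorts have different origins.** Each clock starts at that cohort's first local treatment, the strata are analysed separately, and no survival comparison between them is planned.
- **A reader might take the 5-month column as the expected size.** It requires every gap to be near a limit written for surgical complications, with everyone enrolled late.

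**Conclusion.** The concern holds as a minor point. As written, PFS, OS and time to distant failure in the post-operative cohort are biased upward for patients enrolled after resection, with a weaker effect on local failure.

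The overstatement is about 0.5-2.7 points at 24 months for the planned 3-8 weeks. This rests on a constant hazard, a true rate of 50-80% and everyone enrolled just before radiotherapy, and it scales down with the share enrolled late. The range of 3.8-7.8 points is an upper bound under the same assumptions if every gap were near 5 months. A hazard that is lower soon after surgery would make the bias smaller.

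Primary tests, stopping rules and sample size are untouched. The case for acting is that the error is systematic, one-directional and cheap to remove.

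**What to change.** In Sections 5 and 6.1, keep day of surgery as the origin for the post-operative cohort and state that this is what first day of treatment means there. In Sections 6.1 and 6.3, specify that each post-operative patient enters the risk set at the later of surgery and enrolment, with left-truncated Kaplan-Meier, and left-truncated Cox where a late enrollee contributes. Add how a local failure already present at enrolment is counted, since residual disease does not bar entry.

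Report how many patients enrolled before and after resection, and the numbers at risk from day zero. If nobody enrolled by the day of surgery, label the curve as conditional on being event-free to the earliest entry time.

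Moving the origin to first radiation is simpler, but suits this cohort less well: it drops or mistimes events between surgery and radiotherapy in patients enrolled before resection.

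The cost is a few sentences. Surgery dates are already needed for these endpoints, and Section 12 requires a dated consent form. Estimates will be slightly less favourable, and early risk sets will be smaller, so a single early event can move the curve more.

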Clinical Target Volume 2 (CTV2) is defined as the GTV and the resection bed plus areas that are considered to contain potential microscopic disease which typically would be 5 cm inferior and superior and 2 cm either medially or laterally to the resection bed.

Clinical Target Volume 3 (CTV3) is defined as the GTV and the resection bed plus areas that are considered to contain potential microscopic disease which typically would be 3 cm inferior and superior and 1-2 cm either medially or laterally to the resection bed.

Clinical Target Volume 4 (CTV4) will be determined by the attending radiation oncologist in conjunction with the attending surgeon and will include areas of the resection bed that contain or are thought to be at high risk for positive margins.

Planning Target Volume (PTV) will provide a margin as determined by the attending radiation oncologist around each GTV or CTV to compensate for the variability in treatment set up and internal organ motion.

- Volumes may be modified (reduced) to reflect a compromise between the desired CTV dose to be achieved and the radiation dose limits and the cost-function parameters for the organs at risk.

Normal Structures

The dosimetrist will define two structures: Skin-2 (2mm thick surface) and Skin-PTV (all PTVs will be subtracted from the surface contour). Skin-PTV is the normal tissue structure that is all tissue other than what is contoured as something else.

Organs at risk (OAR) are normal tissue structures in or near the radiation field that may put the patient at risk for toxicities. The OAR volumes are contoured as visualized on the planning scan. Planning OAR is the OAR expanded for setup uncertainty or organ motion. The PAR may be created as determined by the attending radiation oncologist.

Dose fractionation and specification

***Preoperative radiotherapy:* Doses for preoperative radiotherapy will be delivered 1.8-2.0 Gy (RBE)/fx/day delivered to PTV1. The total dose will be 50-50.4 Gy(RBE) to PTV1. A simultaneous in field boost of up to 4-**

CONFIDENTIAL

This material is the property of the University of Pennsylvania. Do not disclose or use except as authorized in writing by the study sponsor

5.4 Gy(RBE) to PTV2 [total dose 54-55.8 Gy(RBE)] may be given as deemed appropriate by the attending radiation oncologist.

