Patient cannot be given treatment because anatomy is such that a dosimetrically satisfactory treatment plan cannot be devised. For example, the dosimetry is unsatisfactory if <95% of target volume is covered by 95% of the dose.

Patient is unable to tolerate 25% of treatments using proton radiotherapy, that is, up to 25% of treatments could be delivered using photons. Reasons for missed treatments may include: unable to set patient up within acceptable limits of tolerance, patient unable to tolerate treatment position or immobilization for duration of treatment).

Patient is unable to complete all of his/her treatments within 10 days of estimated date of treatment completion or requires a treatment break greater than 5 days.

(ii) **Acute toxicity** is defined as any grade 3 or higher hematologic or non-hematologic toxicity that is probably or definitely related to radiotherapy (not surgery). All toxicities observed within 90 days from start of radiotherapy, will be graded by NCI CTC Version 4.0. For pre-operative patients all toxicities observed within 90 days after start of radiation treatment or 30 days after surgery, whichever comes later, will be graded.

Secondary Endpoints:

(i) **Late toxicity** is defined as any grade 3 or higher hematologic or non-hematologic toxicity which occurs after 90 days from start of therapy. Late toxicities will be graded according to the RTOG/EORTC late toxicity criteria. The time frame for late toxicity is open-ended and late toxicities have been known to occur a year or more after therapy. Follow-up for late toxicity will cease when a patient experiences disease progression, since 2nd line therapies may then be initiated.

(ii) **Wound complication** is defined as a secondary operation under general or regional anesthesia for wound repair or wound management without second operation. Wound management includes an invasive procedure without general or regional anesthesia, readmission for wound care such as iv antibiotics, or persistent deep packing for 120 days or longer. Patients will be assessed for wound complications which develop within 4 months after surgery.

(iii) **Fibrosis and joint stiffness** will be graded according to EORTC/RTOG late radiation toxicity criteria. **Edema** will be graded as 0= none, 1= mild, 2= moderate, 3= severe, 4= very severe, according to the criteria of Stern (Stern TN. Clinical examination: a textbook. Year Book Medical

CONFIDENTIAL

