Estimation of Event Rates. The table below displays the 90% exact binomial confidence intervals based on 12 patients treated.

No. of Events	%	90% exact CI	No. of Events	%	90% exact CI
0	0.0	17.5*	7	58.3	31.5 , 81.9
1	8.3	.43 , 33.9	8	66.7	39.1 , 87.7
2	16.7	3.0 , 43.8	9	75.0	47.2 , 92.8
3	25.0	7.2 , 52.7	10	83.3	56.1 , 97.0
4	33.3	12.3 , 60.9	11	91.7	66.1 , 99.6
5	41.7	18.1 , 68.5	12	100.0	82.5*

CONFIDENTIAL

6	50.0	24.5 , 75.5	* 90% 1-sided CI
---	------	-------------	------------------

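### The feasibility rule counts patients treated, but the first infeasibility event is that the patient cannot be treated, so the rule read literally cannot register a planning failure

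*Combined protocol and SAP*

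**What the plan says.** Section 6.1 (Endpoints) scores feasibility patient by patient, and any one of three events makes a patient infeasible. The first is "Patient cannot be given treatment because anatomy is such that a dosimetrically satisfactory treatment plan cannot be devised". The second is failure to tolerate proton delivery for enough of the course, and the third is late completion or a long break. The same three events appear among the feasibility objectives in Section 1, where the study is infeasible if they affect 10% or more of patients. No restriction to treated patients is stated there.

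The decision rule uses a different unit. Section 6.1 (Rules for Early Termination) says "The tables below indicate termination rules after groups of 3 patients have been treated". The feasibility table is indexed by "Patients treated" at 3, 6, 9 and 12, with boundaries "Patients who are feasible 1 4 6 9". The prior is worded the same way: "We will assume a beta (5,1) prior, which is information equivalent to feasibility established in 5 of 6 treated patients". The target is "A feasibility rate > 90% is considered acceptable". The end-of-stage posterior is to be computed as in that table. For the intervals, "The table below displays the 90% exact binomial confidence intervals based on 12 patients treated".

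Section 6.4 says that twelve patients per stratum will be enrolled in the feasibility part, and the synopsis also gives 12 per stratum. Under recruitment in Section 2, a study number is issued once eligibility is established. No listed eligibility criterion requires an acceptable proton plan.

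**The concern.** A patient for whom no acceptable plan exists has, on the plan's own words, not been given treatment. If the rule is run on treated patients, that person is in neither the feasible count nor the denominator. The two delivery events can still register, because they concern patients who have started. The planning event cannot.

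Feasibility is a primary endpoint of this stage and a condition for entering Phase II. Section 6 says that the stage exists partly to gain experience of proton planning and dosimetry. Two analysts could each follow the document and reach opposite decisions on the same data: one from the rule, the other from the endpoint definition.

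**Working it through.** **Inputs.** From Section 6.1: prior beta(5,1), acceptable rate above 0.90, looks at 3, 6, 9 and 12, stop if the feasible count is at or below 1, 4, 6 and 9. From Section 6.4: 12 enrolled per stratum. The documents do not give a planning-failure rate, so 5% to 40% is assumed. The 5% rate of infeasibility for other reasons is also assumed.

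**Reproducing the table.** With x feasible of n, the posterior is beta(5 + x, 1 + n − x), and the quantity needed is Pr(rate > 0.90).

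| Feasible / n | Posterior | Pr(rate > 0.90) | With one more feasible |
|---|---|---|---|
| 1/3 | beta(6,3) | 0.038 | 0.187 |
| 4/6 | beta(9,3) | 0.090 | 0.303 |
| 6/9 | beta(11,4) | 0.044 | 0.158 |
| 9/12 | beta(14,4) | 0.083 | 0.238 |

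Each boundary is the largest count with a posterior below 0.10. The table shows 0.0 in all four cells, which agrees with these values if the second decimal was lost in extraction. The boundaries are sound, and the interval table for 12 patients also reproduces.

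**One data set, two denominators.** Twelve patients are enrolled. Three have no acceptable plan, and nine are treated and feasible.

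- Treated base: 9/9, posterior beta(14,1). Pr(rate > 0.90) = 1 − 0.9^14 = 1 − 0.229 = 0.77. Continue.
- Enrolled base: 9/12 = 75%, posterior beta(14,4). Pr(rate > 0.90) = 0.083. This is the table's own boundary at 12, so termination is considered at that look at the latest.

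**Chance of reaching a boundary.** Let p be the probability that a counted patient is feasible. At each look, add three Bernoulli(p) outcomes to the running count, remove the probability at or below the boundary, and carry the rest forward. The sum of the removed parts is the stopping probability.

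- Failures not counted: p = 0.95. At the first look, 0.05^3 + 3 × 0.95 × 0.05^2 = 0.00725. Over the four looks, 0.00725 + 0.02552 + 0.00177 + 0.00747 = 0.042.
- Failures counted at a 20% planning-failure rate: p = 0.80 × 0.95 = 0.76. Over the four looks, 0.14515 + 0.29703 + 0.05566 + 0.13545 = 0.633.

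| Assumed planning-failure rate | p if counted | Stop, counted | Stop, not counted |
|---|---|---|---|
| 5% | 0.9025 | 0.16 | 0.04 |
| 10% | 0.855 | 0.31 | 0.04 |
| 20% | 0.76 | 0.63 | 0.04 |
| 30% | 0.665 | 0.85 | 0.04 |
| 40% | 0.57 | 0.95 | 0.04 |

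The last column supposes that 12 patients are treated. If enrollment stops at 12 and some are never treated, fewer looks are reached and the figure can only be lower. With no other cause of infeasibility, the counted column is 0.04, 0.16, 0.51, 0.79 and 0.93, and the uncounted column is 0 throughout.

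**The case against.** The best defense is that the word treated is loose shorthand for patients entered. Section 1 speaks of patients without restriction. The endpoint text says that a patient with any listed event is infeasible. Section 6.4 fixes the number enrolled, and the analysis text requires the reasons for infeasibility to be tabulated. The toxicity table carries the same column label, which points to generic wording. Section 1 also provides for photons where protons cannot be delivered. It does so under the second event, but it shows that treated need not mean treated with protons. Finally, the rule says only that termination will be considered.

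Most of this stands as evidence of intent: planning failures were very probably meant to count. It does not repair the rule, because no sentence says that treated means enrolled, or whether a planning failure who then receives photons is treated. The tabulation would make the failures visible but would not put them into the posterior.

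Two stronger readings are tempting. A reader might infer that planning failures are removed and replaced until 12 have been treated. The documents contain no such provision, and the planned feasibility number has no over-enrollment allowance, unlike Phase II, where 50 may be enrolled to obtain 40. A reader might also infer from Section 3, "Volumes may be modified (reduced) to reflect a compromise between the desired CTV dose to be achieved and the radiation dose limits", that coverage is scored on a shrunken target, so that a difficult anatomy passes the first criterion. The plan does not say on which volume coverage is scored. Section 3 gives typical margins and leaves the PTV margin to the radiation oncologist, so there is no fixed unreduced volume to score against.

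**Conclusion.** The point holds as a conflict between the decision rule and the endpoint that it serves. Read literally, the rule is blind to planning failures at any rate, and the same 12 enrolled patients can give 0.77 or 0.083 depending on the denominator. The prior, boundaries, posteriors and intervals are arithmetically correct.

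The practical size depends on a planning-failure rate that the documents do not supply. At an assumed 5%, the stopping probabilities are 0.16 and 0.04; at 20% they are 0.63 and 0.04. If planning failures turn out to be very rare, little changes. It should be corrected because the ambiguity lies in a go/no-go rule on a primary endpoint, but it does not undermine the design. The documents do not support saying that the trial excludes or replaces these patients, or that its feasibility rate will necessarily be biased.

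**What to change.** For the feasibility endpoint only, change the base in the Section 6.1 table, the end-of-stage posterior and the 90% interval from treated patients to patients enrolled in the stratum. State that a patient who meets the first criterion (no satisfactory plan) is scored as not feasible and is not replaced for this endpoint. Reword the prior to match. The boundaries 1/3, 4/6, 6/9 and 9/12 need no recalculation. The acute toxicity and wound complication rules should stay on treated patients, since those events concern people who received treatment.

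The cost is a few sentences of protocol text. The downside is that the reported feasibility rate may be less favorable.
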